12.5.2 Secondary Objectives

12.5.2.1 Function and Strength

TTRW, 6MWT, NSAA, TTCLIMB, and hand-held dynamometer will be summarized by treatment group over time using descriptive statistics.

The TTRW and TTCLIMB times to perform the test will also be converted to velocities. For a test that the participant could not perform, the velocity will be set to zero.

12.5.2.2 Analysis Comparing Viltolarsen to Placebo

TTSTAND, TTRW, 6MWT, NSAA, TTCLIMB, and hand-held dynamometer results will be compared between the viltolarsen treated participants and the placebo treated participants using MMRM analysis with treatment group, week of the visit, and the treatment-by-week interaction as factors, and age as one covariate, and baseline performance as a second covariate. The TTRW and TTCLIMB times to perform the test will be converted to velocities. For a test that the participant could not perform, the velocity will be set to zero.

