2 INTRODUCTION

2.1 Rationale for Study Design, Control Group, and Dose Selection

2.1.1 Rationale for Dose Selection

The dose (80 mg/kg/week for 48 weeks) for this study was based on the successful treatment of participants at 80 mg/kg/week in Study NS-065/NCNP-01-201 for up to a total of 24 weeks of treatment, as well as in the Phase 1/2 Study NS-065/NCNP-01-P1/2 conducted in Japan (Japan P1/2). Results are detailed below.

Viltolarsen dystrophin levels and exon skipping ratio were assessed in Japan P1/2 (Study NS065/NCNP01-P1/2) and Study NS-065/NCNP-01-201. The results are summarized below:

1. Highest dystrophin production measured by Western Blot at 20 to 24 weeks in both Japan P1/2 (Study NS065/NCNP01-P1/2 [n = 4]) and Study NS-065/NCNP-01-201 (n = 8) studies were observed at 80 mg/kg.
2. Average dystrophin production by group measured by Western Blot at 24 weeks in Japan P1/2 (Study NS065/NCNP01-P1/2) was higher at 80 mg/kg (n = 4).
3. Average dystrophin production [REDACTED] measured by Western Blot at 20 to 24 weeks in both Japan P1/2 (Study NS065/NCNP01-P1/2) and Study NS-065/NCNP-01-201 (n = 3) were higher at 80 mg/kg.

[REDACTED]
[REDACTED]
[REDACTED]

4. Average % of dystrophin positive fiber by group measured by immunofluorescence in Study NS-065/NCNP-01-201 was higher at 80 mg/kg (n = 8).
5. Average exon skipping ratio by group measured by RT-PCR in both Japan P1/2 (NS065/NCNP01-P1/2) and Study NS-065/NCNP-01-201 were higher at 80 mg/kg.
6. Safety profiles were comparable in both Japan P1/2 (NS065/NCNP01-P1/2) and Study NS-065/NCNP-01-201 studies between 40 and 80 mg/kg.

Study NS-065/NCNP-01-201) have enrolled a total of 16 participants. As of 28 February 2018, there have been no apparent drug-related serious adverse events (SAEs) reported, and no adverse events (AEs) led to study drug discontinuation. One SAE (left tibia/fibula fracture required hospitalization for surgery, not-related to drug) was reported in June 2018. Safety profiles were comparable for both studies at 40 mg/kg and 80 mg/kg.

In summary, the dose of 80 mg/kg/week for 48 weeks is supported, based on dystrophin production at 80 mg/kg/week and safety profile (well-tolerated for 168 weeks) in the 2 studies (Japan P1/2 (NS065/NCNP01-P1/2) and Study NS-065/NCNP-01-201) conducted to date.

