12.5 Efficacy Endpoints

All efficacy analyses will be performed using the modified intent to treat (mITT) population. In addition, additional analyses will utilize the placebo treatment group.

A hierarchical analysis, following a fixed-sequence hypothesis testing method, is used to first test TTSTAND and then TTRW, 6MWT, NSAA, TTCLIMB, and hand-held dynamometer, if the former was statistically significant.

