12.5.1 Efficacy Objective

The primary efficacy outcome measure (TTSTAND) will be summarized by treatment group over time using descriptive statistics.

The TTSTAND times to perform the test will also be converted to velocities. Note that a test result that is to be converted to velocity that the participant could not perform due to disease progression will have velocity set to zero only at the first visit where this occurs. After that visit, missing observations due to disease progression will be left as missing.

The TTSTAND will be compared between the viltolarsen treated participants and the placebo treated participants using MMRM analysis with treatment group, week of the visit, and the treatment-by-week interaction as factors, and age as one covariate, and baseline performance as a second covariate. The TTSTAND times to perform the test will be converted to velocities.

The treatment comparisons of most interest will be the LS means contrasts between the viltolarsen treated participants and the placebo treated participants at Week 49.

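### The zero-velocity rule for TTRW and TTCLIMB omits the disease-progression limit set for TTSTAND, so read literally an injury at Week 49 counts as complete loss of function on the first gated secondary endpoint

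*Combined protocol and SAP*

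**What the plan says.** Section 12.5.1 (TTSTAND) speaks of results analysed as velocities and says that any such result "that the participant could not perform due to disease progression will have velocity set to zero only at the first visit where this occurs". It then adds: "After that visit, missing observations due to disease progression will be left as missing". The zero therefore depends on the cause, and it is given once.

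Section 12.5.2.1 (descriptive summaries) says: "The TTRW and TTCLIMB times to perform the test will also be converted to velocities". The sentence after it sets the velocity to zero for a test the boy could not perform. Section 12.5.2.2 (treatment comparison) repeats that sentence: "For a test that the participant could not perform, the velocity will be set to zero". Neither section mentions disease progression or a first visit.

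Section 12.5 sets the testing order. The fixed sequence "is used to first test TTSTAND and then TTRW, 6MWT, NSAA, TTCLIMB, and hand-held dynamometer, if the former was statistically significant". Section 12.5.1 places the main comparison at Week 49.

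Section 12.9 rules out imputation unless otherwise specified and leaves the details of missing data to the SAP. Section 12.1 lets the SAP override the protocol. The documents contain no SAP text on this point.

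**The concern.** The same event is handled in two opposite ways, and no rationale is given. A boy in a leg cast at Week 49 cannot rise from the floor, run 10 m or climb stairs. His TTSTAND falls outside the progression rule and stays missing under Section 12.9. His TTRW and TTCLIMB literally meet the condition for a zero.

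Such a zero is an extreme value that says nothing about the course of DMD or the effect of the drug. It moves that arm's mean and inflates the variance. TTRW comes directly after the primary endpoint, so if it fails, 6MWT, NSAA, TTCLIMB and dynamometry cannot be tested. TTCLIMB gates only dynamometry.

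The documents make a leg injury a realistic case. Section 2.1.1 reports from the earlier studies: "One SAE (left tibia/fibula fracture required hospitalization for surgery, not-related to drug) was reported in June 2018". Section 2.2.3 lists increased fracture risk among the effects of glucocorticoids, which inclusion criterion 7 requires every boy to take.

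**Working it through.** **1. The sections side by side, for a leg injury at Week 49**

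- TTSTAND (12.5.1): zero only for disease progression, so the value is missing (12.9).
- TTRW and TTCLIMB (12.5.2.1, 12.5.2.2): could not be performed, so velocity = 0.
- Section 12.9 does not remove the zero, because the zero rule is itself something otherwise specified.
- Sections 9.15.1.2 and 9.15.1.5 provide for recording the seconds taken, not the reason a test was not done.

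**2. The plan's own figure**

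Section 12.2 gives difference 0.05, SD 0.075, two-sided alpha 0.05, power 0.8 and 1:1 allocation, with an unpaired t-test. The standardised effect is 0.05/0.075 = 0.667. The exact noncentral-t power is 0.797 at 36 per arm and 0.808 at 37 per arm, so 37 per arm (74 in total) reproduces. That figure is not in dispute.

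**3. Inputs for TTRW**

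- From the documents: 37 per arm and the final-stage alpha of 0.049 (Section 12.8).
- Assumed: a standardised TTRW effect of 0.667 (borrowed from TTSTAND), and a ratio R of placebo mean to SD between 3 and 8. For example, a mean of 2 m/s (10 m in 5 s) with SD 0.67 gives R = 3, and with SD 0.25 gives R = 8.
- Simplification: an unpaired t-test stands in for the MMRM.

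**4. Shift in the estimated difference, in SD units**

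- One zero on viltolarsen: 0.667 − (R + 0.667)/37. For R = 3 this is 0.667 − 0.099 = 0.568. For R = 8 it is 0.667 − 0.234 = 0.433.
- One zero on placebo: 0.667 + R/37. For R = 3 this is 0.748. For R = 8 it is 0.883.

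In both cases the pooled SD also rises.

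**5. Simulated power (40,000 trials per cell)**

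With no false zero, power is 0.805.

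| R | One zero on viltolarsen | One zero in each arm | One zero on placebo |
|---|---|---|---|
| 3 | 0.610 | 0.700 | 0.863 |
| 4 | 0.528 | 0.639 | 0.871 |
| 5 | 0.428 | 0.558 | 0.871 |
| 8 | 0.158 | 0.277 | 0.855 |

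If the same boys are left missing, power is about 0.80 with one missing and 0.794 with one missing per arm (exact, 36 per arm). The expected difference stays at 0.667.

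**6. No true effect, one zero on placebo**

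Two-sided rejection is about 0.04 to 0.05 for R from 3 to 8, against a nominal 0.049. Most of those rejections favour viltolarsen (about 0.04 to 0.05, against 0.049/2 = 0.0245), and the other direction loses the balance. Two placebo zeros with none on viltolarsen are needed before two-sided rejection reaches about 0.07 to 0.09.

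**The case against.** **The TTSTAND rule may be meant to cover all three tests.** Its wording in Section 12.5.1 is generic: it speaks of any result to be converted to velocity. The sentences in 12.5.2.1 and 12.5.2.2 could then be shorthand for it. This reading is possible, so the documents do not establish that the sponsor intends to score injuries as zero. However, the rule sits in the TTSTAND section, and its first-visit limit is also absent from the later sections. The sections conflict and need reconciling under either reading.

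**The SAP may settle it.** Section 12.1 allows that, but no SAP text on the point is available, and the protocol text would still need repair.

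**Refusal and acute illness.** A reader might extend the rule to a young boy who refuses, or one too ill to attempt the test. The text does not clearly support this. Refusing is not being unable, and a test never attempted may simply be missing under Section 12.9. The boundary is undefined. Only the injury case fits squarely.

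**Frequency.** A reader might take one fracture among 16 boys as a rate and expect one or two affected boys among 74. Section 2.1.1 gives no follow-up time for that fracture, and a fracture at any time is not the same as inability at the Week 49 visit. It shows plausibility only.

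**False gain.** A reader might infer that a placebo zero creates false positives. One such zero does not raise two-sided type I error above nominal, as step 6 shows.

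**Size.** The power figures rest on assumed values and a simplified test. That stands, so only a range is given.

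**Conclusion.** The inconsistency is real on the current text. Sections 12.5.2.1 and 12.5.2.2 attach no cause to the zero, while Section 12.5.1 limits it to disease progression. Applied literally, a leg injury at Week 49 becomes complete loss of function on TTRW and TTCLIMB.

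Under the stated assumptions (37 per arm, effect 0.667 SD, t-test, R from 3 to 8), one such zero on viltolarsen cuts TTRW power from about 0.80 to between 0.16 and 0.61. One in each arm cuts it to between 0.28 and 0.70. One on placebo raises power to about 0.86 to 0.87 and inflates the estimated difference from 0.67 to between 0.75 and 0.88 SD. These are illustrations of sensitivity, conditional on such an event occurring; its probability cannot be derived from the documents.

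The consequence is limited to the secondary endpoints. TTSTAND is unaffected, and TTRW is tested only if TTSTAND succeeds. The point should be corrected before database lock.

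**What to change.** In Sections 12.5.2.1 and 12.5.2.2, and in the SAP, replace the zero-velocity sentence with: *Velocity is zero if the participant was unable to do the test because of disease progression; if the test was not done for any other reason, the value is missing.*

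Reconcile this with Section 12.5.1: say whether its rule covers all three velocity endpoints, and whether the first-visit limit applies to TTRW and TTCLIMB. Have the blinded clinical evaluator record the reason at the visit on the existing function-test eCRF page.

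The cost is one sentence, one eCRF field, a few more missing values, and a blinded judgement of the reason, which Section 12.5.1 already requires for TTSTAND. In the illustration above, leaving the values missing costs about one percentage point of power or less.

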12.6 Safety Assessments

Safety analyses will be performed using the safety population. All safety assessments will be based on actual treatments received by participants and are detailed in the protocol and statistical analysis plan.

12.6.1 Anthropometrics, Vital Signs, Laboratory Assessments, and ECG

Anthropometrics, vital signs, hematology, chemistry, urinalysis, and ECG results will be summarized by treatment over time using descriptive statistics for continuous outcomes. Actual values and change from Day 1 will be presented. Further, all laboratory abnormalities will be listed.

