The fraction of viltolarsen bound to rat, monkey, and human serum proteins was low, $\leq 40\%$, for all species and was independent of concentration. The distribution of viltolarsen into red blood cells was $\leq 2.5\%$, $\leq 6.7\%$, and $\leq 3.5\%$ for rat, monkey, and human, respectively, indicating low distribution of viltolarsen to red blood cells. Quantitative whole-body autoradiography (QWBA) studies showed wide tissue distribution of [^{14}C] viltolarsen in both mice and monkeys, with the highest concentrations observed in the kidney, and general distribution to muscle tissues. For both rats and monkeys, renal excretion was the major route of elimination, with less than 10% in the feces. No radioactivity was in the expired air from the rats. Most of the radioactivity was excreted within the first 24 hours. However, small measurable amounts continued to be excreted in the urine and feces throughout the seven-day collection periods.

Viltolarsen showed weak inhibition to cytochrome (CYP) 3A4 (K_i value: 1.44 mmol/L), while no inhibitory effects were observed to other CYPs (CYP1A2, CYP2B6, CYP2C8, CYP2C9, CYP2C19 and CYP2D6). Viltolarsen did not induce CYP1A2, CYP2B6 and CYP3A4. Viltolarsen showed weak inhibition to UGT1A1 (K_i value: 0.642 mmol/L), while no inhibitory effects were observed to UGT2B7. Viltolarsen was not a substrate of transporters (P-gp, BCRP, OAT1, OAT3, OCT2, MATE1 and MATE2-K). Viltolarsen showed weak inhibition to OATP1B1, OATP1B3, OAT3 and BCRP (respective IC_{50} value: 0.485, 0.448, 0.176 and 1.97 mmol/L), while no inhibitory effects were observed to other transporters (P-gp, OAT1, OCT1, OCT2, MATE1, MATE2-K and BSEP).

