Histopathological evaluations following a single IV dose of 600 mg/kg in monkeys resulted in vacuolation of the epithelium of the proximal renal tubules. No other renal changes were noted. Repeated administration of viltolarsen via the clinically relevant route of administration (weekly IV injections) in mice, rats and monkeys resulted in decreases in red blood cell parameters, increased values for cytokines and histopathological effects in the kidney and urinary bladder. The kidney is the primary target organ in mice, rats and monkeys, as shown by increased values in clinical chemistry parameters indicative of renal effects (1000 mg/kg in 4-, 13- and 26-week mouse studies, ≥ 500 mg/kg in 4- and 13-week rat studies, and 600 mg/kg in a 12-week monkey study) and by histopathological findings of effects in renal tubules (≥ 240 mg/kg in 4-, 13- and 26-week mouse studies, ≥ 250 mg/kg in 4-week and 13-week rat studies ≥ 200 mg/kg in 12- and 39-week monkey studies) accompanied by increased kidney weight at necropsy. An additional histopathological finding in a 26-week mouse study was the presence of cytoplasmic eosinophilic material in the transitional epithelium of the urinary bladder at 60 mg/kg and above. An increase in blood urea nitrogen (BUN) was observed in all toxicity studies with all species mainly at the higher doses. The main causes of an increase in BUN are high protein diet, decrease in glomerular filtration rate (GFR) (suggestive of renal failure) and in blood volume (hypovolemia), congestive heart failure, gastrointestinal hemorrhage, fever, and increased catabolism. In the toxicity studies with viltolarsen, BUN increases were considered to be attributable to a decrease in GFR. Based on these data, the no observed adverse effect levels (NOAELs) were concluded to be 60 and 15 mg/kg in 13-week and 26-week mouse studies respectively and 60 mg/kg in 12-week and 39-week monkey studies respectively. Results from *in vitro* and *in vivo* genotoxicity studies were negative, and studies showed no evidence of chromosomal aberrations.

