2.3.3 Summary of Clinical Findings

A Phase 1 investigator-initiated study (Study NCNP/DMT01) ([ClinicalTrials.gov NCT02081625](#)) of viltolarsen injection was conducted in DMD patients (aged 5 to 18 years) to investigate the overall usefulness of viltolarsen injection in the treatment of DMD, based on evaluations of safety, exploration of predictive markers of treatment response, and assessment of PK. A total of 10 DMD patients were enrolled and randomized. IV administration of viltolarsen injection in doses of 1.25 mg/kg, 5 mg/kg and 20 mg/kg to DMD patients once weekly for 12 weeks was well tolerated, and no dose-limiting toxicity was observed, although all patients had at least one AE. Moreover, neither SAEs nor incidences of Common Terminology Criteria for Adverse Events (CTCAE) v4.0-JCOG (Japanese translation, published by the Japan Clinical Oncology Group [JCOG]) Grade 3 (severe) or worse were reported.

Among the mild and moderate AEs, an increase in beta-N-acetyl-D-glucosaminidase (Grade 1) was found in all patients in both cohorts 1 and 2 [Cohort 1 (n = 3) Cohort 2 (n = 3)] and in all but one patient in Cohort 3 [Cohort 3 (n = 4)].

Initially, testing appeared to reveal proteinuria in 8 of 10 patients. However, it was subsequently determined that there was a cross reaction between viltolarsen and the pyrogallol red dye-binding method, which was used for urinary protein measurement resulting in a false positive result for protein in the 24-hour pooled urine samples. To evaluate the 24-hour pooled urine samples for protein, the Coomassie brilliant blue method was used to re-measure urinary protein in the frozen urine samples. None of the retested samples showed urinary protein levels exceeding the normal range of the institution (i.e., 31.2 to 120 mg/day). [REDACTED]

[REDACTED]

[REDACTED]

[REDACTED]

The 24-hour pooled urine samples did not show increased levels of albumin. Spot measurements of urinary albumin were positive in 7 patients (Grade 1).

Interleukin levels were increased (Grade 1) in the serum in 6 out of 10 patients (high IL-6 level in 4 subjects, high IL-1 β level in 1 subject, and high IL-2 level in 1 subject), and some level of anemia (Grade 1) was observed in 7 out of 10 patients.

Increased levels of brain natriuretic peptide (Grade 1) in serum were present in 4 patients. White blood cell count (WBC) was increased in 3 patients (Grade 1). All other mild and moderate AEs occurred in 2 or fewer patients.

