 - Dipstick protein (to be performed by the site on the first morning void urine samples)
- 24-Hour Urine Analysis
 - Protein (benzethonium chloride method)
 - Creatinine
- Urine Cytology
- Glomerular Filtration Rate (via Exogenous Tracer Test)

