10.1.2 Pre-Infusion Visit (Days -7 to -1)

- Review of inclusion/exclusion criteria
- Concomitant medications and treatment history; any changes will be noted
- Height and weight
- Vital signs
- Physical and neurological examination
- First morning void urinalysis

Note: Analysis of the first morning void urine sample will include urine dipstick protein to be performed at the site.

- Urine cytology (utilizing a urine sample collected on-site)
- Exogenous tracer GFR

Note: This should be done, if possible, per standard of care at the institution.

- Function and strength
 - TTSTAND
 - TTRW
 - NSAA
 - TTCLIMB
 - Hand-held dynamometer
 - 6MWT

- Patient reported outcomes
 - PODCI
 - PARS III Questionnaire
- AE review

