10.2.1 Day 1 Dosing Visit (First Infusion)

The following assessments will occur:

- Confirmed diagnosis of DMD
- Concomitant medications and treatment history; any changes will be noted
- Height and weight
- 12-lead ECG
- Vital signs
- Physical and neurological examination
- Hematology
- Chemistry
- Postdose urinalysis (utilizing a urine sample collected within 5 hours after completion of the infusion)
- Anti-dystrophin antibody (predose)
- Anti-viltolarsen antibody (predose)
- PK blood sample (pre and postdose)
- Investigational product administration

- AE review

10.2.2 Week 2

The following assessments will occur:

- Review of medical and surgical procedures, concomitant medications, and other treatments; any changes will be noted
- Vital signs
- Investigational product administration
- AE review

10.2.3 Week 3

The following assessments will occur:

- Review of medical and, surgical procedures, concomitant medications, and other treatments; any changes will be noted
- Vital signs
- Hematology
- Chemistry
- First morning void urinalysis

Note: Analysis of the first morning void urine sample will include urine dipstick protein to be performed at the site.

- Investigational product administration
- AE review

10.2.4 Week 4

The following assessments will occur:

- Review of medical and surgical procedures, concomitant medications, and other treatments; any changes will be noted
- Vital signs
- Investigational product administration
- AE review

10.2.5 Week 5

The following assessments will occur:

- Review of medical and surgical procedures, concomitant medications, and other treatments; any changes will be noted
- Vital signs
- Physical and neurological examination
- Hematology
- Chemistry
- First morning void urinalysis

Note: Analysis of the first morning void urine sample will include urine dipstick protein to be performed at the site.

- Investigational product administration
- AE review

10.2.6 Weeks 6 to 8

The following assessments will occur:

- Review of medical and surgical procedures, concomitant medications, and other treatments; any changes will be noted
- Vital signs
- Investigational product administration
- AE review

10.2.7 Week 9

The following assessments will occur:

- Review of medical and surgical procedures, concomitant medications, and other treatments; any changes will be noted
- Vital signs
- Physical and neurological examination
- Hematology
- Chemistry

- First morning void urinalysis

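### Section 12.6.1 measures urinalysis change from Day 1, but the only urine scheduled on Day 1 is collected after the first infusion

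*Combined protocol and SAP*

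**What the plan says.** Section 12.6.1 lists urinalysis with anthropometrics, vital signs, hematology, chemistry and ECG as results to be described by treatment over time. It then adds: "Actual values and change from Day 1 will be presented". It gives no predose qualifier and makes no exception for urine.

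The urine item in the Day 1 visit list (Section 10.2.1) reads: "Postdose urinalysis (utilizing a urine sample collected within 5 hours after completion of the infusion". Table 1 marks no other urine sample on Day 1, and its footnote s gives the same collection window.

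The last pre-drug urinalysis is at the Pre-Infusion Visit (Section 10.1.2, Days -7 to -1), where a note says: "Analysis of the first morning void urine sample will include urine dipstick protein to be performed at the site". Table 3 ties dipstick protein to that specimen type: "Dipstick protein (to be performed by the site on the first morning void urine samples".

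Sections 9.14.1 and 11.11.1 include a trigger of UPCR at least twice baseline, but do not name the baseline visit. Section 12.1 says that the SAP will be finalised before database lock and overrides the protocol where the two differ. The supplied file contains no separate SAP text.

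**The concern.** A change score is meant to remove each boy's pre-treatment level. If the reference sample is taken after the first dose, any acute urinary effect of that dose enters the reference value in the viltolarsen arm only. Randomisation does not cancel it. An acute rise would make later changes in that arm look smaller, and an acute fall would make them look larger.

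Urine findings matter for this drug. In the non-clinical summary (Section 2.3.2), "The kidney is the primary target organ in mice, rats and monkeys", and "For both rats and monkeys, renal excretion was the major route of elimination". In Phase 1 (Section 2.3.3), "an increase in beta-N-acetyl-D-glucosaminidase (Grade 1) was found in all patients in both cohorts 1 and 2", and in all but one of the four patients in cohort 3. That is 3 + 3 + 3 = 9 of 10 patients, at doses of 20 mg/kg or less; this trial gives 80 mg/kg. Those rises were Grade 1, and the summary describes no control group. They are a reason to want a clean change table, not evidence of harm.

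**Working it through.** The plan gives no figure to reproduce. The check sets the analysis rule beside the sampling schedule.

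1. **Urine on Day 1** (Table 1, footnote s, Section 10.2.1). Predose urinalyses: 0. Postdose urinalyses: 1. Dipstick protein values: 0, because dipstick is done on first morning voids and none is scheduled that day.

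2. **Timing of the Day 1 sample.** The infusion lasts 1 hour (Section 5.2.2), so the sample falls between 1 and 6 hours after the start. The Phase 1 plasma half-life was 1.52 to 1.84 hours (Section 2.3.3). The latest permitted sample is therefore 5/1.84 = 2.7 to 5/1.52 = 3.3 half-lives after the end of infusion. In the viltolarsen arm the reference is always post-drug.

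3. **Later urinalyses per boy** (Tables 1 and 2).
   - First morning voids: Weeks 3, 5, 9, 13, 17, 21 (6) and Weeks 25, 29, 33, 37, 41, 45, 49 (7), total 13.
   - Postdose samples: Weeks 13, 25 and 37, total 3.
   - Share compared with a different specimen type: 13/(13 + 3) = 81%. For 74 boys this is 13 × 74 = 962 of 16 × 74 = 1,184 scheduled samples.

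4. **Effect on the between-arm comparison.** Write V and P for the arm means of a urine measure, t for a later visit and D1 for Day 1. The difference in mean change is (V_t − P_t) − (V_D1 − P_D1). With a pre-drug reference, the second bracket has expectation zero by randomisation. With the postdose reference it equals the acute effect of the first dose, d, so the table shows the later effect minus d. The documents give no value for d, so neither the size nor the direction of the bias can be computed.

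5. **Effect of specimen type.** A shift between a morning void and a daytime post-infusion sample that is common to both arms cancels between arms on an additive scale. It still remains in each arm's own change column, which then mixes time with specimen type.

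6. **The three later postdose samples.** Their Day 1 reference is the same specimen type, so only the post-drug problem applies to them.

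7. **Available alternative.** The Pre-Infusion Visit supplies one pre-drug first morning void, with dipstick. It matches 13 of the 16 later samples in type.

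**The case against.** The strongest reply is that Day 1 is shorthand that was not adapted for urine. Section 12.4 plans a summary of baseline safety characteristics that includes urinalysis. The UPCR rule sits within text about first morning voids, and the only pre-drug one is at the Pre-Infusion Visit. Baseline definitions are ordinary SAP content, and the SAP overrides the protocol. This makes a drafting slip more likely than a deliberate choice of a post-drug baseline. It does not remove the problem, because none of these sections names the urine baseline visit and the one explicit rule says Day 1.

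Three stronger readings are tempting, and the documents do not support them.

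- A reader might infer that lasting renal harm would be hidden. Section 12.6.1 also plans actual values by arm and a listing of all laboratory abnormalities, and both would still show a lasting rise. The fixed triggers in Section 11.11.1 (dipstick 2+ or more, UPCR 0.5 mg/mg or more, 24-hour protein 300 mg/day or more) do not use a baseline.
- A reader might infer that dipstick protein has no baseline at all. It lacks only a Day 1 value. It is also semi-quantitative, whereas Section 12.6.1 describes continuous outcomes, so a change summary for it is not clearly planned.
- A reader might carry over the Phase 1 finding that "there was a cross reaction between viltolarsen and the pyrogallol red dye-binding method" and expect false protein values on Day 1. Table 3 specifies a different method (benzethonium chloride), so that artefact need not recur. On retesting, no Phase 1 24-hour sample exceeded the normal range for protein.

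The 16-boy extension study also reported no sign of treatment-related kidney toxicity (Section 2.3.3).

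**Conclusion.** The point holds as a fault in a stated rule. Taken literally, Section 12.6.1 gives the viltolarsen arm a post-drug reference for every urine change, and a mismatched specimen for 13 of 16 later urinalyses in both arms. The consequence is confined to descriptive change columns. The primary analysis, by-arm actual values, abnormality listings and fixed-threshold renal triggers do not depend on it.

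The mismatch count follows directly from the visit schedule. The extent of any bias would require an assumed acute effect, for which the documents give no basis, so none is claimed. The conclusion rests on the protocol text alone. A SAP that defines the urine baseline as the last pre-drug first morning void would settle it.

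**What to change.** In Section 12.6.1, or in the SAP before database lock if it does not already say so:

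1. For urinalysis, replace change from Day 1 with change from baseline, and define baseline as the Pre-Infusion Visit first morning void. Use the same definition for the criterion of UPCR at least twice baseline in Sections 9.14.1 and 11.11.1.
2. Summarise the postdose urinalyses (Day 1 and Weeks 13, 25 and 37) separately by arm, as actual values.
3. For vital signs and ECG, which have both predose and postdose readings on Day 1 (Sections 9.9 and 9.10), state that the predose value is the reference.

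The cost is a few sentences and a minor change to table programming. The sample is already scheduled for every boy, so no visit, specimen or participant is added.
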